2.3.1.1 Medical Examinations

Medical examinations, including phlebotomy for blood analysis are not associated with more than minimal risks. There is usually some discomfort when the needle is inserted for phlebotomy.

2.3.1.2 Radiation Exposure

Radiation exposure in this protocol will be from $[^{18}\text{F}]\text{SF12051}$ and the associated transmission scans. With our PET/CT scan, the effective doses for one head and one whole-body transmission scans 0.02 and 0.6 rem respectively. In addition, we routinely include the dose from two transmission scans in the event that it must be repeated in a subject. The effective dose from two head CT scans is 0.04 rem (and from four CT scans in case of test-retest acquisition is 0.08 rem) and from two whole body scans is 1.2 rem. The radiation exposure from $[^{18}\text{F}]\text{SF12051}$ is unknown, but ^{18}F -labeled compounds generally show very similar dosimetric values of about 20 $\mu\text{Sv}/\text{MBq}$ (0.074 rem/mCi) ([10](#)) or about 0.37 rem for a 5 mCi injection.

Please note that no pharmacological effects are expected from $[^{18}\text{F}]\text{SF12051}$. Therefore, only radiation risks are relevant to this tracer.

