1.2 SCHEMA

Abbreviated Title: [¹⁸F]SF12051 in Healthy Subjects

Version Date: 12/05/23

Schedule of Activities (SOA)

This study will require 1-4 visits for each participant depending on the phase in which they are in. An initial blood sample to determine TSPO binding genotype will be acquired under protocol 01-M-0254 “The Evaluation of Patients with Mood and Anxiety Disorders and Healthy Participants”. The first visit for each phase will encompass a screening evaluation that includes H&P, lab tests and EKG. Subsequent visits will include an MRI and/or a PET scan, in order of earliest availability, and arterial line for the volunteers in the primary study with brain PET scans. If possible, MRI and PET scans can be done on the same day to limit to two or three total visits. The MRI and PET visits will take approximately 2 and 6 hours, respectively. For dosimetry, two total visits are sufficient due to lack of MRI.

This protocol is a first-in-human evaluation of [¹⁸F]SF12051 and has four phases:

- a) Phase 1: whole body PET imaging of one [1] subject with a low injection activity of ~2 mCi to confirm that no organ has prominently high uptake of [¹⁸F]SF12051;
- b) Phase 2: kinetic brain PET imaging in ten [10] subjects with up to 5 mCi injection to quantify TSPO in brain relative to concurrent measurement of the parent radioligand in arterial plasma;
- c) Phase 3: if [¹⁸F]SF12051 is successful in Phase 2 in the first couple of subjects, we will estimate the radiation-absorbed doses by performing whole body PET imaging on up to ten [10] subjects, with 5 mCi injection;
- d) Phase 4: test-retest brain PET analysis in up to twenty-four [24] subjects, of brain binding relative to concurrent measurement of the parent radioligand in arterial plasma (5 mCi per scan).

Thus, a total of 11 participants for whole body imaging and 34 participants for brain imaging.

Table 1 for Phases 1 and 3

| | 1 st Visit / Screen | 2 nd Visit |
|-------------------------------------|--------------------------------|-----------------------|
| Informed Consent | X | |
| History and physical exam | X | |
| Screening lab tests* | X | |
| EKG | X | X |
| Pregnancy test (female subjects) | x | X |
| Whole-body PET with venous sampling | | X |
| Safety tests for PET scans** | | X |
| Follow-up phone call | | X |

* The screening lab tests are described in Section 8.1.2.

** Safety tests for each PET scan are described in Section 8.3

Table 2 for Phases 2 and 4

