5.6.2 Compensation

Participants will be compensated for time- and research-related inconveniences. Reimbursement is based on NIH standards for time devoted to the research project. Participants will be paid for each portion of the study they complete whether or not they opt for early withdrawal from participation. Without incomplete study procedures or unanticipated inconvenience, the total possible compensation for procedures is \$220 for Phases 1 and 3, \$390 for Phase 2, and \$650 for Phase 4. These compensation amounts do not account for time spent at the NIH, for which the first hour of each visit is compensated \$20 and every subsequent hour is compensated \$10. Payment will be submitted after completion of each visit to NIH through direct deposit. If the investigators need to delay study procedures or if additional time is need for completion, participants may receive additional compensation in accordance with NIH guidelines.

Due to last-minute cancellations, appointments may be scheduled within 72 hours' notice. Participants who are scheduled for appointments on short notice may be eligible for a bonus payment of \$250 if they are scheduled and complete a visit with less than 72 hours' notice.

Outpatient participants will receive support for travel, meals, and lodging according to NIH travel policy guidelines. Lodging may be provided directly or reimbursed according to NIH guidelines. Employees and staff who participate during work hours must have permission from their supervisor. NIH employees must either participate outside of work hours or take leave in order to receive compensation.

Subjects undergoing Dosimetry Whole-body Scan (Phases 1 and 3)

| | |
|-----------------------|-------|
| Visit 1 to NIH | |
| Screening | \$20 |
| Pregnancy test | \$10 |
| Visit 2 to NIH | |
| PET scanning | \$150 |

Abbreviated Title: [¹⁸F]SF12051 in Healthy Subjects

Version Date: 12/05/23

| | |
|------------------------------|---------------|
| Antecubital venous catheters | \$30 |
| Pregnancy test | \$10 |
| Movement restriction | \$10 |
| Total | \$230* |

Subjects undergoing Brain Scan (Phase 2)

| | |
|------------------------------|---------------|
| Visit 1 to NIH | |
| Screening | \$20 |
| Pregnancy test | \$10 |
| Visit 2 to NIH | |
| PET scanning | \$150 |
| Arterial catheter | \$60 |
| Antecubital venous catheters | \$30 |
| Pregnancy test | \$10 |
| Movement restriction | \$10 |
| Visit 3 to NIH | |

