8.2.1 PET Procedures

Radioligand

[¹⁸F]SF12051 will be administered via an indwelling intravenous catheter over ~1 minute, within four hours after synthesis of the radioligand. The radioligand is stable during this period.

Insertion of the intravenous line

An intravenous line will be placed in the arm. The venous line will be used to inject the radioligand and will be removed at the end of the day. The IV line may be replaced if it fails to remain patent.

PET acquisition for brain and/or lung imaging

PET scans will be performed using a PET/CT or the HRRT. The choice of the scanner for a particular study will depend on scanner availability. Participants will be placed on the scanner bed with their head held firmly in place with a thermoplastic mask or a head holder fixed to the bed. A transmission scan will be performed before the PET scan to measure and correct for attenuation. Tracer infusions will be performed in the nuclear medicine department, while the subject is on the scanner bed.

After an intravenous bolus of about 5 mCi, arterial blood samples will be drawn from the arterial catheter during the PET scan. We will collect about 20-25 arterial samples. First, blood samples will be drawn every 15 seconds after injection for about 3 to 5 minutes, and then they will be collected every 5, 10, 15, or 30 minutes. The total amount of arterial blood will be about 100 mL. PET images of the brain will be acquired in three-dimensional mode with increased length of frame for a total of 120 minutes. The duration may be shortened on the basis of the results of time stability analysis.

At the end of the scans, the arterial and venous lines will be removed, and the subject will be instructed to void frequently to minimize radiation exposure.

PET acquisition for dosimetry

Whole body dosimetry scans will be performed with a PET/CT. The choice of the scanner for a particular study will depend on scanner availability. No arterial sampling will be done for dosimetry studies. Both a pre-injection transmission scan and a series of dynamic emission scans will be acquired. Each subject will be imaged in contiguous segments from the top of the head to a point below the gonads. To minimize extraneous motion, all subjects may wear a head-holding mask and will have their arms and abdomen wrapped with body-restraining sheets. This may add some additional discomfort. Venous samples up to 30 mL may be obtained

Abbreviated Title: [¹⁸F]SF12051 in Healthy Subjects

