Version Date: 12/05/23

to measure [¹⁸F]SF12051 levels. Before injection of the radioligand, a transmission scan will be acquired for subsequent attenuation correction. Then, an initial set of dynamic emission scans will be acquired following the intravenous injection of [¹⁸F]SF12051. The acquisition of each cycle will begin with an emission scan at the first bed position (i.e., the head), and continue by moving the bed distally to the next body segment. Then, a second transmission scan, identical to the first, will be performed followed by a second set of dynamic emission scans.

Arterial Line Placement

For brain scans, a radial artery catheter will be inserted by the NIH Clinical Center Anesthesiology Department, after the presence of adequate ulnar collateral flow has been established. The skin at the site of the puncture will be anesthetized with 1% lidocaine. The catheter will be perfused (3 mL/h) with heparin solution (600 units/L) during the procedure. The amount of heparin infused will be much smaller than the amount necessary to produce any systemic anticoagulant effect.

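### Section 2.3.1.2 presents 1.2 rem of whole-body CT as including a repeat, but Section 8.2.1 schedules both scans; one repeat takes Phase 3 from 1.57 to 2.17 rem

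*Combined protocol and SAP*

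**What the plan says.** Section 2.3.1.2 (Radiation Exposure) gives an effective dose of 0.02 rem for one head and 0.6 rem for one whole-body transmission scan on the PET/CT. It then explains that "we routinely include the dose from two transmission scans in the event that it must be repeated in a subject". The resulting figures are 0.04 rem for two head CTs and, continuing, "from four CT scans in case of test-retest acquisition is 0.08 rem) and from two whole body scans is 1.2 rem". The tracer dose is stated separately, as about 0.37 rem for 5 mCi.

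Section 8.2.1 (PET Procedures) describes what is done. For dosimetry, "Whole body dosimetry scans will be performed with a PET/CT", so each transmission scan is a CT. The sequence opens with "Before injection of the radioligand, a transmission scan will be acquired for subsequent attenuation correction". After the first emission set it continues: "Then, a second transmission scan, identical to the first, will be performed followed by a second set of dynamic emission scans". For brain imaging the same section schedules only one: "A transmission scan will be performed before the PET scan to measure and correct for attenuation".

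Phases 1 and 3 share this dosimetry procedure: Table 1 in Section 1.2 and the compensation schedule in Section 5.6.2 treat them together. There is one imaging visit after screening ("For dosimetry, two total visits are sufficient due to lack of MRI"), so both CTs fall in the same session.

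**The concern.** Two whole-body CTs are counted in Section 2.3.1.2 on the reasoning that one is planned and one is held in reserve. Section 8.2.1 uses both as a matter of routine. A reader of the risk section would take 1.2 rem as the CT total with a repeat already covered. In fact a failed CT that has to be redone adds another 0.6 rem, which appears in no stated total.

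This is the largest radiation item in the study. Participants are healthy volunteers with no direct benefit (Section 2.3.2), and Section 2.3.1.2 itself treats radiation as the only relevant risk of the tracer. Exclusion criterion 8 (Section 5.2) also requires this study's dose to be added to recent exposure and compared with the allowable limits. If the Section 2.3.1.2 figures are used for that sum, a volunteer could be admitted whom a repeat CT would take over the limit.

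**Working it through.** **Inputs**

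- Whole-body CT 0.6 rem, head CT 0.02 rem (Section 2.3.1.2).
- Tracer 20 µSv/MBq, a generic value for ¹⁸F compounds; the dose for this tracer is unknown (Section 2.3.1.2).
- Injected activity: about 2 mCi in Phase 1 and 5 mCi in Phase 3 (Section 1.2); the clinician may approve half the prescribed dose, 2.5 mCi (Section 6.1.2).
- CTs scheduled: two per whole-body session, one per brain PET scan (Section 8.2.1).

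**Step 1: reproduce the stated figures**

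- Head: 2 × 0.02 = 0.04 rem; 4 × 0.02 = 0.08 rem.
- Whole body: 2 × 0.6 = 1.2 rem.
- Tracer: 20 µSv/MBq × 37 MBq/mCi = 740 µSv/mCi = 0.074 rem/mCi; × 5 mCi = 0.37 rem.

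All agree with the protocol.

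**Step 2: compare CTs counted with CTs scheduled**

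| Imaging | Scheduled (8.2.1) | Counted (2.3.1.2) | Spare |
|---|---|---|---|
| One brain scan | 1 | 2 | 1 |
| Test-retest brain (two scans) | 2 | 4 | 2 |
| Whole-body dosimetry | 2 | 2 | 0 |

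Only the whole-body figure lacks the allowance that the text describes.

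**Step 3: totals**

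Total = (number of CTs × 0.6) + (mCi × 0.074). The protocol does not print these sums; they follow from its figures.

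| Case | Tracer (rem) | Two CTs, as scheduled | Three CTs, one repeat | Increase |
|---|---|---|---|---|
| Phase 3, 5 mCi | 0.370 | 1.57 | 2.17 | 38% |
| Phase 3, 2.5 mCi | 0.185 | 1.385 | 1.985 | 43% |
| Phase 1, 2 mCi | 0.148 | 1.348 | 1.948 | 45% |

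As a sensitivity range, assume the tracer dose per mCi is 0.5 to 1.5 times the generic value. Phase 3 at 5 mCi is then 1.385 to 1.755 rem as scheduled and 1.985 to 2.355 rem with one repeat. The difference is 0.60 rem in every case.

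**Step 4: context**

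- Phase 2, spare head CT included: 0.04 + 0.37 = 0.41 rem.
- Phase 4, spare head CTs included: 0.08 + 2 × 0.37 = 0.82 rem.
- CT share of scheduled Phase 3 dose: 1.2 / 1.57 = 76%.
- People concerned: 1 (Phase 1) + up to 10 (Phase 3) = up to 11.

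The Phase 2 and 4 figures assume the PET/CT. Section 8.2.1 also allows the HRRT for brain scans, and no transmission dose is given for it.

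**The case against.** The strongest reply is that no stated dose is wrong. Two whole-body CTs do give 1.2 rem, two are scheduled, and the per-scan dose is printed, so a reader could add a third. That is correct, and it limits the point: planned exposure is not understated. It does not rescue the repeat clause, which credits the whole-body figure with a reserve it does not have.

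A second reply is that 2.17 rem depends on how many spares are counted. This also stands. One repeat per session is the smallest allowance. One spare per planned scan, as in the head figures, would mean four CTs, or 2.4 + 0.37 = 2.77 rem in Phase 3. That reading widens the gap.

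Third, the opening overview of dosimetry acquisition in Section 8.2.1 mentions only a pre-injection transmission scan. It does not exclude a second one, and the detailed sequence that follows schedules it without condition. If one CT were really intended, Section 8.2.1 would be the text to correct.

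Fourth, the harm is conditional. It needs a repeat CT, a volunteer with recent exposure, use of these figures for exclusion 8, and a limit lying within the 0.6 rem gap. The documents give no repeat frequency, numeric limit or counting method. The Radiation Safety Committee's own accounting is not among them. All of this is true, and no breach is claimed.

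**Conclusion.** The point holds. The 1.2 rem in Section 2.3.1.2 is the scheduled whole-body CT dose and contains no repeat allowance, contrary to the explanation given beside it. One repeat adds 0.60 rem: Phase 3 goes from 1.57 to 2.17 rem (+38%) and Phase 1 from 1.35 to 1.95 rem. This affects at most 11 volunteers, and only those whose CT is repeated.

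The totals rest on the protocol's generic tracer dose; the 0.60 rem difference does not. The conclusion takes the detailed sequence in Section 8.2.1 as the governing description. It should be corrected because it is a wrong statement about the study's largest exposure in people who cannot benefit. It is not evidence that any limit is exceeded.

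**What to change.** Preferred: in Section 2.3.1.2, state for whole-body imaging two scheduled CTs (1.2 rem) plus one repeat (0.6 rem), 1.8 rem in all. The totals become 2.17 rem for Phase 3 and 1.95 rem for Phase 1, and these should be used when exclusion criterion 8 is applied.

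Alternative: keep 1.2 rem, state in Section 8.2.1 that whole-body CTs will not be repeated, and limit the repeat wording in Section 2.3.1.2 to head scans.

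Either way the cost is a short amendment with IRB approval; the first option also needs Radiation Safety Committee review of the higher figure. It may exclude a few more volunteers who have had recent research scans. Under the second, a failed CT could lose some or all of that participant's dosimetry data, although if only the second CT fails, the first CT and first emission set are already complete. Scan schedule, sample size and analysis do not change.

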2.3.1.3 PET Scanning

PET scans, which detect injected radioactivity within the body, are not associated with any known physical hazards to the participant lying on the table. We routinely use a series of procedures to minimize the risk of discomfort during scanning sessions. The procedures are

conducted in the presence of trained health professionals to whom participants will have ready access should they experience any problems. Participants can communicate with the trained health professionals while in the scanner and can be removed from the scanner and withdraw from the study at any time if they wish to do so. Participants can also request that the operator stop the scan.

2.3.1.5 Blood Sampling

Participants may have arterial or venous blood sampling. The total amount of blood drawn shall not exceed 10.5 mL/kg or 550 mL, whichever is smaller, over any eight-week period. Blood sampling may lead to the formation of small subcutaneous hematomas caused by blood leaking from a punctured blood vessel. Such hematomas cause only minor discomfort. They are not dangerous and require no treatment other than reassuring the participant. There is also a small risk of infection at the site of the needle puncture, which can be readily treated with antibiotic therapy. We will ask participants not to donate blood within eight weeks before the study or for eight weeks following the study.

2.3.1.6 MRI

People are at risk for injury from the MRI magnet if they have pacemakers or other implanted electrical devices, brain stimulators, some types of dental implants, aneurysm clips (metal clips on the wall of a large artery), metallic prostheses (including metal pins and rods, heart valves, and cochlear implants), permanent eyeliner, an implanted delivery pump, or shrapnel fragments. Welders and metal workers are also at risk for injury because of possible small metal fragments in the eye of which they may be unaware. Participants will be screened again for these conditions before having any scan and will not receive an MRI scan if they have any contraindications.

It is not known whether MRI is completely safe for a developing fetus. Therefore, all women of childbearing potential will have a urine pregnancy test performed no more than 24 hours before each MRI scan. The scan will not be done if the pregnancy test is positive.

People with fear of confined spaces may become anxious during an MRI. Those with back problems may have back pain or discomfort from lying in the scanner. The noise from the scanner is loud enough to damage hearing, especially in people who already have hearing loss. Everyone having a research MRI scan will be fitted with hearing protection. Participants will be

Abbreviated Title: $[^{18}\text{F}]\text{SF12051}$ in Healthy Subjects

Version Date: 12/05/23

asked to complete an MRI screening form for each MRI scan they have. There are no known long-term risks associated with MRI scans.

2.3.1.7 EKG

The patient may feel uncomfortable while the electrodes are attached to the chest. The conductive gel sometimes causes some mild irritation.

2.3.2 Known Potential Benefits

This study offers no direct benefits to participants. Information obtained from this protocol study may improve our understanding of the pharmacokinetics and usefulness of a new TSPO tracer.

2.3.3 Assessment of Potential Risks and Benefits

This study will determine the viability of $[^{18}\text{F}]\text{SF12051}$ as a prominent radiotracer for TSPO in vivo imaging. If successful, this radiotracer can be a more stable alternative for future TSPO imaging studies as compared to the currently used ^{11}C counterpart. The risks are reasonable in relation to anticipated benefit.

The ways in which the study design aims to minimize risks, please reference each risk detailed above (see Section 2.3.1).

3 OBJECTIVES AND ENDPOINTS

| OBJECTIVES | ENDPOINTS | JUSTIFICATION FOR ENDPOINTS |
|---|--|--|
| Primary | | |
| To evaluate the brain uptake of $[^{18}\text{F}]\text{SF12051}$ in healthy volunteers and perform kinetic modeling of the $[^{18}\text{F}]\text{SF12051}$ in the three different TSPO genotypes | Receptor density measured as distribution volume (V_T) | V_T is the 'gold standard' method to measure receptor density. |
| Secondary | | |
| To study retest variability and reliability of $[^{18}\text{F}]\text{SF12051}$ | Receptor density measured as distribution volume (V_T) | The two key parameters for retest studies are variability and reliability. |
| To study the biodistribution and dosimetry of $[^{18}\text{F}]\text{SF12051}$ in healthy subjects | Radiation burden to organs of the body | We follow the FDA standards for calculating radiation burden. |

Abbreviated Title: [¹⁸F]SF12051 in Healthy Subjects

Version Date: 12/05/23

4 STUDY DESIGN

4.1 OVERALL DESIGN

- **Site:** This single-site study will be conducted at the NIH Clinical Center.
- **Hypothesis:** We hypothesize that [¹⁸F]SF12051 will have satisfactory distribution regardless of genotype, acceptable retest variability and reliability, and dosimetry typical of ¹⁸F-labeled radioligands.
- **Phase:** Phase 1
- **Type of Design:** Study is neither randomized nor placebo-controlled; exploratory study.
- **Study Groups:** Healthy volunteers
- **Study intervention:** Brain and body PET scans with [¹⁸F]SF12051 and brain MRI.
- **Interim Analysis:** None
- **Stratifications:** None

4.2 SCIENTIFIC RATIONALE FOR STUDY DESIGN

This study is to evaluate the efficacy of a novel radioligand and could provide useful information for other studies investigating TSPO in the future.

4.3 JUSTIFICATION FOR DOSE

Studies with novel ¹⁸F-radioligands typically inject 5 mCi i.v., which is enough to measure both radioactivity in brain with PET and the concentration of parent radioligand in arterial plasma.

5 STUDY POPULATION

5.1 INCLUSION CRITERIA

To be eligible to participate in this study, an individual must meet all of the following criteria:

1. Aged 18 years or older.
2. Healthy based on medical history, physical examination, and laboratory testing.
3. Able to provide informed consent.
4. Willing and able to complete all study procedures.
5. Have been screened for TSPO genotype under 01-M-0254 “The Evaluation of Patients with Mood and Anxiety Disorders and Healthy Participants”.
6. Have their radial artery pulse checked for the presence of adequate ulnar collateral flow and the absence of any metal or foreign objects in both wrists*.
7. Agree to adhere to the lifestyle considerations (see Section [5.4](#))

*Does not apply to Phase 1 and 3 participants as they will not have an arterial line.

Abbreviated Title: [¹⁸F]SF12051 in Healthy Subjects

Version Date: 12/05/23

